- c. Behavioral assessments will be carried out by trained interviewers/therapists ([name], M.S.W., [name], M.A., [name]., [name], M.A., [name], M.A., [name], M.S.W.) under the supervision of [name].
- d. Computer-assisted Behavioral Therapy. Monitoring and discussion of the computer delivered coping skills treatment program will be carried out by trained interviewers/therapists ([name], M.S.W., [name], M.A., [name]., [name], M.A., [name], M.A., [name], M.S.W.) under the supervision of [name].

General Design:

155 subjects whom meet criteria for cocaine dependence, and all other study inclusion and

NEW YORK STATE PSYCHIATRIC INSTITUTE INSTITUTIONAL REVIEW BOARD

exclusion criteria (described above) will begin a 4-week computer-assisted behavioral intervention. Those participants not responding to the behavioral intervention will begin a 10-week double-blind, placebo-controlled treatment trial. Subjects will be randomized to receive either placebo or MAS-ER. Table 1 shows the overall design

1. Design Overview

We will investigate the effect of augmenting a self-directed version of the Community Reinforcement Approach (CRA; Budney & Higgins, 1998) with Mixed Amphetamine Salts-Extended Release (MAS-ER) to improve treatment response among cocaine dependent patients who do not benefit from the behavioral intervention alone. Patients who do not respond by week four of the CRA+CM intervention will be randomized to a 10-week double blind design to test the combined effects of CRA+CM/MAS-ER against a CRA+CM/PLACEBO control condition. Participants who are randomized to the combination behavioral treatment and medication arm (CRA+CM/MAS-ER) will have their dose titrated to 60 mg MAS-ER daily (over 2 weeks) and maintained on this dose through week 13 of the trial. During week 15, participants will be tapered off the medication (see Table 1. below). Patients responding to the CRA+CM intervention in the first four weeks of treatment will continue with the behavioral intervention and be assessed in parallel to the two (CRA+CM/MAS-ER and CRA+CM/PLACEBO) enhanced treatment arms.

Randomization: Those patients randomized to the placebo group will continue to receive CRA+CM and placebo throughout the treatment. Patients randomized to the CRA+CM/MAS-ER group will begin receiving medication at the start of week 5 and will receive a stable dose of MAS-ER by study week 7.

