Dosing Schedule: Subjects will take capsules (PBO or MAS-ER) as titrated in Table 2 below.

Medication Lead-out: During week 15 patients assigned to active medication have their medication tapered. The purpose of the placebo lead-out is to keep patients blind to the exact point of medication discontinuation, and afford systematic observation of effects of medication discontinuation.

27 Week Outcome: Twelve weeks after study completion (27 weeks after enrollment) an attempt will be made to evaluate all participants to explore whether there may be effects of treatment that endure or emerge after medication discontinuation. In exploratory analyses, outcome at 27 weeks will be compared among three groups: those originally assigned to continue behavioral therapy alone, patients assigned to receive either medication or placebo. Group comparisons will be conducted on the main primary and secondary outcomes.

Medication: MAS-ER, and matching placebo will be prepared by our pharmacy at the NYSPI,

NEW YORK STATE PSYCHIATRIC INSTITUTE INSTITUTIONAL REVIEW BOARD

packaged in matching gelatin capsules with lactose filler in each capsule. The research pharmacist, who has no contact with patients, is the only non-blind member of the research team. At each weekly visit the psychiatrist orders the dose of double-blind medication for the coming week according to the schedule (shown in Table 2). The psychiatrist will adjust the dose according to tolerability. MAS-ER or matching placebo will be given in a fixed-flexible dose schedule with the MAS-ER dose titrated to 60 mg per day.

MAS-ER or matching placebo will be taken once per day in the morning or early afternoon since it may be activating. The medication will be packaged in gelatin capsules with lactose filler plus **25 mg** of riboflavin. MAS-ER or matching placebo are given in a "fixed-flexible" dose schedule with the dose titrated to 60 mg per day or the maximum tolerated dose. The standard dose titration will be 10 mg per day for the days 8-9, 20 mg per day for days 10-12, 30 mg per day for days 13-14, 40 mg per day for days 15-18, 50 mg per day for days 19-21 and 60 mg for the remainder of the study. MAS-ER is FDA approved for the treatment of ADHD in doses up to 60 mg per day.

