If a patient does experience any uncomfortable side effects, the dose will not be raised, and if necessary, the dose will be lowered. If the patient cannot tolerate at least 20 mg/day of MAS-ER the medication will be discontinued. Patients will be encouraged to set a quit date three weeks after starting study medications (the end of the titration phase of MAS-ER). During week 14 patients on active medication will be **tapered off MAS-ER**.

Planned/unplanned absences that would require the patient to be given more than one week worth of medications will be considered on a case-by-case basis. In the case of unplanned absences, up to one week of medication can be shipped via FedEx with signature upon receipt. This will allow patients who miss their scheduled appointments to remain on stable medication.

We will evaluate the adequacy of the double-blind by asking patients which treatment drug they thing they are receiving. The blinded nurse will also be asked to report which drug s/he thinks each patient is taking. The research staff (i.e., therapist, nurse, research assistant and psychiatrist) that administers medications and/or conducts interviews and assessments will be blind to medication condition, urine toxicology results, and medication blood levels during the course of the 10-week trial. The non-blinded pharmacist will be the only ones who have access to this information during the trial. However, a sealed envelope will be kept in a locked office if the Principal Investigator needs to break the blind in an emergency situation. At the completion of the 10-week trial, or at the conclusion of the patient's involvement in the trial (if they do not complete all 10 weeks), patients will learn their treatment assignment.

Computer-assisted CRA with Contingency Management: All consented patients will begin the trial receiving CRA+CM delivered in a computer-assisted treatment format. Patients will be asked to attend the clinic 3 times per week for urine toxicology, and on 2 of those occasions, participate in a 30-40 minute session using the self-directed version of the Community Reinforcement Approach (CRA+CM). CRA+CM is a well-established skills oriented treatment for cocaine dependence that utilizes tangible incentives to promote abstinence (Budney & Higgins, 1998). This treatment has

Protocol Summary Form 6850 [name]

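### Completers learn their arm at the end of week 14, before the week-15 lead-out meant to be blind, and the narrative leaves the week-14 dose ambiguous

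*Protocol*

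**What the plan says.** On disclosure, the blinding paragraph of the protocol's Medication section has patients learn their assignment when the 10-week trial is complete, or when they leave if they stop sooner. The same paragraph words the blind for clinical and research staff as lasting for the 10-week trial. An earlier paragraph of that section says that the research pharmacist "is the only non-blind member of the research team" and sets no time limit.

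On the lead-out, the Medication Lead-out paragraph says: "The purpose of the placebo lead-out is to keep patients blind to the exact point of medication discontinuation". It adds a second aim, to "afford systematic observation of effects of medication discontinuation".

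On the taper and the last full dose, four places speak:

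- Design Overview: 60 mg is "maintained on this dose through week 13 of the trial", and then "During week 15, participants will be tapered off the medication".
- Medication Lead-out: "During week 15 patients assigned to active medication have their medication tapered".
- Medication, dose titration: "50 mg per day for days 19-21 and 60 mg for the remainder of the study".
- Medication, paragraph on tolerability: "During week 14 patients on active medication will be" tapered off MAS-ER.

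The SAP defines the primary outcome over Phase 2, weeks 5-14 (C10). It takes the last assessment of the exploratory cognitive and coping measures at week 14 (C13) and analyses their change from week 5 to week 14 (C14).

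**The concern.** A lead-out that hides when the drug stops does its work only while patients are uncertain. If they have just been told their arm, a placebo patient knows there is nothing to withdraw from, and a MAS-ER patient knows that a taper is due or has just happened. Sleep, mood, craving and side-effect reports in that week are then open to expectation, so the observation of discontinuation effects is no longer blind.

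The taper wording is a separate matter. The study psychiatrist orders a controlled stimulant week by week against a schedule, so the last full-dose week should be unmistakable. Week 14 is also the last week of the primary window and the closing assessment for the mechanism measures. Depending on the schedule meant, those measures are taken at full dose or during a taper, and a reader of the results would need to know which.

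**Working it through.** **Timing of disclosure.** Inputs: medication starts at the start of week 5 (Protocol, Randomization); the double-blind phase lasts 10 weeks (Design Overview); follow-up is 12 weeks after study completion and 27 weeks after enrollment (27 Week Outcome); there are 45 visits at 3 per week (Compensation; Medication).

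1. Last week of the 10-week phase: 5 + 10 − 1 = 14. This reproduces the weeks 5-14 of SAP C10.
2. Last week of the protocol: 27 − 12 = 15, and 45 / 3 = 15. Both agree with the 15-week protocol named under Treatment to be provided at the end of the study.
3. Gap: 15 − 14 = 1 week, which is the lead-out week and holds 3 of the 45 visits (3/45 = 6.7%).
4. Could the 10-week trial include week 15? Weeks 5 to 15 number 15 − 5 + 1 = 11, not 10. The disclosure sentence also speaks of patients who do not finish all ten weeks, so ten is a count.

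Disclosure as written therefore comes before the lead-out week.

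**Week-14 dose.** Three schedules, set against the statements in the text:

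| Statement | Taper in week 15 only | Taper in week 14, placebo in week 15 | One taper across weeks 14-15 |
|---|---|---|---|
| 60 mg through week 13 | stops a week short | fits | fits |
| Taper in week 15 (two places) | fits | conflicts | fits |
| Taper in week 14 | conflicts | fits | fits |
| 60 mg for the rest of the study | fits only if the study means weeks 5-14 | conflicts | conflicts |

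No schedule satisfies every sentence literally. The third satisfies all the statements that name a week, but the text never sets it out. The second agrees best with calling the lead-out a placebo lead-out.

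**How the two matters combine.** Under the first schedule the whole taper follows disclosure. Under the third, its second week does. Under the second, the taper is finished before disclosure and only the placebo week is affected. In every case week 15 is spent knowing the arm.

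**Reach of week 14.** It is 1 of the 10 weeks of the primary window. The endpoint is a yes/no record of at least 3 consecutive abstinent weeks, so a patient who has completed such a run before week 14 is unaffected. Only a patient whose sole qualifying run needs days in week 14 could be affected. The documents give no figure for that share, so no effect on the response rates can be calculated.

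**The case against.** The case on the other side has four parts.

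First, the governing schedule is in Tables 1 and 2. Design Overview points to Table 1 for the taper, and the psychiatrist orders doses from Table 2. Both are uploads that cannot be seen here. This stands: the text shows an ambiguity in wording, and one might go on to infer a dosing failure in practice, which the documents do not support.

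Second, the lead-out is meant to hide the stopping point, not the assignment. A MAS-ER patient who knows the arm may still not know the exact day. This stands in part. It does not help on the placebo side, nor with the second aim of observing discontinuation effects.

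Third, no planned analysis is shown to suffer. The SAP names no week-15 endpoint, C12 gives no window for the secondary outcomes, and the 27-week comparison comes after disclosure in any case. This stands and limits the weight of the point. What is lost is an aim that the protocol itself states.

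Fourth, a reader might infer that staff too are unblinded in week 15, because the staff-blind sentence covers only the 10-week trial. The documents do not support that: the statement on the pharmacist has no end date. The two sentences should simply agree.

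**Conclusion.** The plan as written discloses assignment one week too early for its own lead-out. That follows from the calendar and holds under any of the three taper schedules. The narrative also leaves the week-14 dose open, subject to what Tables 1 and 2 show.

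The consequences are limited. Early disclosure affects 3 of 45 visits and the blind observation of discontinuation, not a named SAP endpoint. The week-14 ambiguity bears on how the week-14 mechanism measures are described and, to a small extent that cannot be quantified, on the primary outcome.

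A reader might infer that the primary comparison is biased, or that several points of the assumed 37% response rate hang on the week-14 dose. Neither is supported. The window is the same in both arms, an earlier taper would be part of the regimen being compared, and nothing in the documents says how many responders would first qualify in week 14. Both changes below should be made; neither calls the primary analysis into question.

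**What to change.** (a) Tell completers their assignment only after the week-15 lead-out assessments are done, and keep the sealed-envelope emergency code break. State that staff stay blind to medication condition through week 15, in line with the statement on the pharmacist. Limit that extension to medication condition: the present sentence also covers urine toxicology, which sits awkwardly with on-site testing and immediate feedback to patients. The cost is about one week's wait for completers. The supportive therapy and referral offered at the end of the 15-week protocol are not delayed.

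(b) Make Design Overview, Medication Lead-out and Medication state the single taper schedule given in Tables 1 and 2. Name the last full-dose week in place of the open-ended 60 mg wording. If week 14 falls in the taper, say in SAP C13 and C14 that the week-14 measures are taken during taper. This is wording only if the schedule chosen is the one in the tables. If it is not, it is a dosing change: tapering in week 15 only, instead of in week 14, would add up to one week at 60 mg.

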Once screening is completed, there is no delay for study entry for eligible patients.

NEW YORK STATE PSYCHIATRIC INSTITUTE INSTITUTIONAL REVIEW BOARD

The patient should receive the behavioral treatment treatment within 2 weeks after the initial screening evaluation. For those who the behavioral intervention alone will not work, will be randomized to a medication treatment arm 4 -weeks after beginning the treatment, if they have been randomized to the active medication arm. Those assigned to the placebo group will not receive active medication, but will continue to receive the behavioral treatment. CRA+CM is an evidenced based treatment program for the treatment of cocaine dependence.

Maximum duration of delay to standard care or treatment of known efficacy

Because the screening procedure sometimes requires 2-3 meetings, individuals may not begin the computer-assisted CRA+CM therapy until 2-3 weeks after their initial screening evaluation for the study.

Treatment to be provided at the end of the study

At the conclusion of the 15-week protocol, the participants will be offered supportive therapy for at least one additional month or until an appropriate referral for on-going treatment is made.

If a patient was on active medications and they were shown to be beneficial, they will be given an appropriate referral for ongoing treatment.

Clinical Treatment Alternatives

Clinical treatment alternatives

Psychotherapeutic approaches are commonly used for encouraging reduction in use or abstinence of drugs of abuse in general. There are no accepted pharmacotherapies for the treatment of cocaine dependence. These approaches include motivational enhancement and cognitive behavioral therapy, 12-step facilitation, and other methods. Alternative treatment settings for substance abuse include drug free outpatient treatment, inpatient detoxification, or residential treatment. Patients will be informed that they can request referrals for other treatment options.

Risks/Discomforts/Inconveniences

Risks that could be encountered during the study period

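### Patients are due to learn their arm at the end of week 14, before a lead-out that one part of the Protocol places in week 15, and before a 27-week comparison that is nowhere described as unblinded

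*Protocol*

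**What the plan says.** **Disclosure.** The Medication section of the Protocol sets the time as "At the completion of the 10-week trial, or at the conclusion of the patient's involvement in the trial", if that comes before week 10 of the trial. At that time "patients will learn their treatment assignment". The same paragraph promises staff blinding to medication condition only for the duration of the 10-week trial, and keeps a sealed envelope for emergencies.

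**Trial calendar.** Under General Design, participants "will begin a 4-week computer-assisted behavioral intervention", and non-responders then enter a "10-week double-blind, placebo-controlled treatment trial". The Randomization paragraph says the active arm "will begin receiving medication at the start of week 5". SAP C10 defines Phase 2, the primary outcome window, as weeks 5-14.

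**Lead-out.** The Medication Lead-out paragraph places the taper in week 15 and states: "The purpose of the placebo lead-out is to keep patients blind to the exact point of medication discontinuation". It gives a second purpose, systematic observation of the effects of stopping. The Design Overview also puts the taper in week 15, but describes the maintenance dose as continuing only through week 13. The Medication section puts the taper in week 14.

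**Follow-up.** The 27 Week Outcome paragraph plans to evaluate all participants 12 weeks beyond study completion. In exploratory analyses, "outcome at 27 weeks will be compared among three groups" on the primary and secondary outcomes. The Ongoing medical assessment section repeats the plan as medication versus placebo and adds Addiction Severity Index composite scores.

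**Aftercare.** Supportive therapy and referral are set at a later point than disclosure: "At the conclusion of the 15-week protocol".

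**The concern.** A lead-out that hides when active drug stops works only while patients do not know what they are taking. If assignment is disclosed one week earlier, a placebo patient knows there is no drug to stop. An active patient knows that any change felt that week may be withdrawal. Reports of use and side effects in that week could then reflect expectation as well as pharmacology.

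The same applies, over a longer interval, at week 27. That visit is meant to look for effects that persist or appear after medication ends. Several of its outcomes rest wholly or partly on what the patient says: timeline follow-back cocaine use, craving and quality of life. The withdrawal scale (CSSA) is clinician-rated, so it depends on staff blinding, which is promised only for the 10-week trial. If patients know their arm and the report does not say so, an arm difference at week 27 could be read as a lasting drug effect when expectancy is an equally good explanation.

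**Working it through.** No power or sample-size formula enters. The check is calendar arithmetic plus a comparison of sections.

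1. **Reproduce the Protocol's own follow-up date.** Inputs: a 15-week protocol (Treatment to be provided at the end of the study) and a visit 12 weeks after completion (27 Week Outcome). 15 + 12 = 27, which matches the stated week 27. Counting from week 14 would give 14 + 12 = 26, which does not match. Study completion is therefore week 15. The compensation section agrees: 45 visits over 15 weeks is 45 / 15 = 3 per week, so visits and urine collection continue through week 15.

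2. **Date of disclosure for completers.** A 4-week run-in plus 10 weeks double-blind: 4 + 10 = 14. Medication starts in week 5 and SAP C10 ends Phase 2 at week 14, so disclosure falls at the end of week 14.

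3. **Position of week 15.** 15 - 4 = 11. Week 15 is the 11th week after the run-in, and so lies outside the 10-week trial and after disclosure.

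4. **Sections on the taper, side by side.**

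| Section | Maintenance dose | Taper |
|---|---|---|
| Design Overview | through week 13 | week 15 |
| Medication Lead-out | not stated | week 15 |
| Medication | not stated | week 14 |

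Tables 1 and 2, which might settle this, are not in the text supplied.

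5. **Consequence under each reading.**
   - Lead-out in week 15: it begins after completers are told their arm. Masking is lost for placebo patients and weakened for active patients.
   - Lead-out wholly in week 14: it precedes disclosure, and the point falls for completers.

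6. **Interval to the 27-week visit.** For completers, 27 - 14 = 13 weeks after disclosure. It is longer for a patient told on leaving earlier; for example, 27 - 5 = 22 weeks for one whose involvement ended at the end of week 5. This holds under both readings in step 5.

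**The case against.** The strongest reply is that the lead-out point depends on a disputed date. If the Medication section is right that the taper is in week 14, which fits a dose held through week 13, completers are told after the taper and nothing is lost. That stands, and it is why this half of the point is conditional.

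It can also be said that the lead-out masks the moment of stopping and not the arm. An active patient who knows the arm may still not know the day on which active drug stops, and discontinuation effects can still be observed. That stands too. A reader might infer that disclosure defeats the lead-out altogether, but the text supports only loss of masking for placebo patients and weakening for active patients.

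Three further inferences are tempting and not supported:

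- **That about 32 patients would be unblinded on leaving early.** 100 - 68 = 32, but the 100 randomised (SAP C7) is 2 x 50, the 90% power case in SAP C8. The 68 completers required is 2 x 34, the 80% power case. The difference is a gap between two power scenarios. The documents state no dropout rate.
- **That patients who stop medication are told at once.** The Protocol ties disclosure to the end of involvement in the trial and does not say how soon it follows. A patient who stops capsules but keeps attending may still be involved and blind.
- **That early leavers should wait until week 15.** That would still leave them informed 27 - 15 = 12 weeks before the 27-week visit, so it would not blind that comparison.

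Finally, the 27-week comparison is labelled exploratory, and the SAP describes no week-15 or week-27 analysis. The text supplied does not show which scales, if any, are scheduled in week 15. These facts limit the importance of the point but do not remove it: the Protocol gives both the lead-out and the 27-week visit a stated purpose, and knowledge of assignment bears on each.

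**Conclusion.** The point holds in a limited form. As written, completers learn their arm at the end of week 14. If the lead-out is in week 15, as the Design Overview and the Medication Lead-out paragraph say, it is run on patients who know their assignment. If it lies wholly in week 14, that part does not apply to completers. The documents do not resolve which is meant.

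The second part does not depend on the taper week. The 27-week comparison by assigned arm is made 13 weeks after completers are told, and later still relative to disclosure for those told sooner. No section describes it as unblinded.

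A reader might infer that the primary result is compromised. For completers it is not, because the window of weeks 5-14 closes before they are told. What is affected is the interpretation of the lead-out observations and of an exploratory follow-up comparison. The conclusion assumes that the 10-week trial means weeks 5-14, as the SAP states, and that the tables not supplied do not set a different disclosure date.

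**What to change.** 1. Reconcile the Design Overview, Medication Lead-out and Medication sections on the week of the taper and lead-out, and check them against Tables 1 and 2.
2. For patients still attending, move routine disclosure to after the last week-15 assessment. Keep the emergency envelope, and allow earlier disclosure where clinical care needs it.
3. Extend the stated blinding of research staff to medication condition, now limited to the 10-week trial, to the same point.
4. State in the Protocol and SAP that the 27-week comparison is unblinded, and that its self-reported outcomes will be interpreted with that in mind.

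No change is proposed for patients who have already left the trial.

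The cost is a few sentences in the Protocol and consent form, and completers wait about one week longer (15 - 14 = 1). That wait fits the Protocol's own timing, since supportive therapy and referral are already placed at the end of the 15-week protocol. The change does not blind week 27; for that visit it only makes the status of the data explicit.
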